## 6 ANALYSIS POPULATIONS

### 6.1 Safety Analysis Set

The safety analysis population will consist of all enrolled subjects who receive at least 1 dose of KRN23 (full or partial injection) during the study.

### 6.2 Pharmacodynamic Analysis Set

The pharmacodynamic (PD) analysis set consists of all subjects who receive at least 1 dose of study drug and who have evaluable plasma/serum data.

### 6.3 Efficacy Analysis Set

All efficacy analyses (other than the PD analyses) will be performed on all subjects who receive at least 1 dose of study drug and who have at least one pre- and post-treatment measurement.

## 7 DATA SCREENING AND ACCEPTANCE

### 7.1 Handling of Missing and Incomplete Data

Missing clinical outcome data can occur for multiple reasons, including missed subject visits and scales or measures with missing item scores. Missing and incomplete data will be identified through a review of tables and listings for this study. Missing and incomplete data will be identified for investigation, and possible resolution, by Data Management prior to the study database lock.

For all analyses, missing data will be treated as missing, unless otherwise specified. When a change from baseline is assessed, only subjects with a baseline and at least one post-baseline measurement will be included in the analysis.

Depending on the number of discontinuations and missed visits from the study, a sensitivity analysis might be conducted for the pharmacodynamics and the efficacy endpoints analyses, where missing data will be imputed using mBOCF (modified Baseline Observation Carried Forward) defined as follows:

- for discontinuations due to AE or death use the worst between BOCF (Baseline Observation Carried Forward) and LOCF (Last Observation Carried Forward)
- otherwise use LOCF.

### 7.2 Missing data in WOMAC questionnaire

For computing the domain scores at each visit for each subject, the WOMAC missing data algorithm is as follows:

1. If two or more Pain items, both Stiffness items, or four or more Physical Functioning items are missing, then the corresponding scale score is set to missing.
2. Otherwise, any missing item is replaced with the mean of the other items in its scale, and scales are then calculated normally.

### 7.3 Missing data in SF36 questionnaire

The SF-36v2 missing data algorithm for computing the domain scores from responses to individual items is property of QualityMetric, and is not available for further description.

### 7.4 Missing Date Imputation Rules

The following conventions will be used to impute missing portions of dates for adverse events and concomitant medications. Note that the imputed values outlined here may not always provide the most conservative date. In those circumstances, the imputed value may be replaced by a date that will lead to a more conservative analysis.

1. Start Dates

1. If the year is unknown, then the date will not be imputed and will be assigned a missing value.
2. If the month is unknown, then:
  1. If the year matches the first dose date year, then impute the month and day of the first dose date.
  2. Otherwise, assign 'January.'
3. If the day is unknown, then:
  1. If the month and year match the first dose date month and year, then impute the day of the first dose date.
  2. Otherwise, assign the first day of the month.

2. Stop Dates

1. If the year is unknown, then the date will not be imputed and will be assigned a missing value.
2. If the month is unknown, then assign 'December.'
3. If the day is unknown, then assign the last day of the month.

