7.5.3.3 Prior and Concomitant Medications/Therapies

Subjects will be asked whether medication to suppress PTH (e.g., Sensipar®, cinacalcet, calcimimetics) has been taken within 2 months before the Screening Visit; subjects who must continue to take PTH suppressors will be excluded from the study, or, if medically able to discontinue PTH suppressors, the subject may be enrolled after a 2-month washout period. Likewise, a 21-day washout of any active pharmacologic vitamin D metabolite or its analog (e.g., calcitriol, doxercalciferol, and paricalcitol), phosphate, and aluminum hydroxide antacids (e.g., Maalox® and Mylanta®) is required for inclusion if medically able to discontinue those medications. Live (attenuated) vaccines (except influenza vaccines) are prohibited within 3 months prior to Screening through the EoT Visit.

All other medications (investigational, prescription, over-the-counter, and herbal) and nutritional supplements taken within 30 days before the Screening Visit will be reviewed and recorded. Throughout the study, investigators may prescribe any concomitant medications or treatments deemed necessary to provide adequate supportive care except those listed in Section 7.5.3.3.1. Therapies (physical therapy, occupational therapy as well as mobility and walking devices, including ankle foot orthoses (AFOs), braces, cane, crutches, walker, wheelchair etc.) used within 30 days before the Screening Visit and at Baseline will also be reviewed and recorded.

Concomitant medications and therapies while on treatment will be reviewed and recorded in the subject's eCRF beginning on the day of initial dosing (Baseline, Week 0) (indication, start date, stop date, dose, dose regimen), at all clinic and HH visits, and at the follow-up telephone call. At each subsequent visit, change in medications and therapies since the previous visit will be recorded on the concomitant medication pages in the subject's eCRF. Throughout the study, there should be no significant changes to a subject's diet or medication schedule unless medically indicated. Investigators may prescribe any concomitant medications or treatments deemed necessary to provide adequate supportive care, except those listed in Section [7.5.3.3.1](#).

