### 8.6.1 Adverse Events

Reported adverse event (AE) terms are coded to MedDRA (version 18.1). All reported events will appear in AE listings, however only TEAE will be summarized. TEAEs are defined as AEs with onset on or after the time of initiation of study drug administration.

The following AEs will be summarized:

- All TEAEs
- Related TEAEs
- Events to monitor:
  - Injection site reactions
  - Gastrointestinal events
  - Immunogenicity
  - Ectopic mineralization
  - Hyperphosphatemia
  - Restless legs syndrome
- Grade 3/4 TEAEs
- Serious TEAEs
- Serious related TEAEs
- TEAEs resulting in discontinuation
- Fatal TEAEs.

Summaries of TEAEs will show incidence rates for each MedDRA primary SOC and PT.

All TEAEs will be tabulated in the following manner: by system organ class/preferred term in descending order, by system organ class/preferred term/relationship to study drug, and by system organ class/preferred term/severity. Additionally, treatment-emergent SAEs and TEAEs related to investigational drug will be tabulated by system organ class/preferred term in descending order.

Injection site reactions (ISR) will be listed for PT, seriousness, severity, outcome, relationship to study drug, and onset time from investigational product administration.

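### Partial AE start dates are set to the first-dose date without checking a known earlier stop date, so an AE that ended before dosing can be counted as treatment-emergent

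*SAP*

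**What the plan says.** SAP 7.4 states its scope as follows: "The following conventions will be used to impute missing portions of dates for adverse events and concomitant medications". Two of its start-date branches lead to the first-dose date:

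- Day missing: "If the month and year match the first dose date month and year, then impute the day of the first dose date". Otherwise the first of the month is used.
- Month missing: "If the year matches the first dose date year, then impute the month and day of the first dose date". Otherwise January is used.

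Neither branch refers to the stop date, and nothing else in the section requires the start to precede the stop. The one qualifier is that "the imputed value may be replaced by a date that will lead to a more conservative analysis".

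SAP 8.6.1 then classifies events by onset only: "TEAEs are defined as AEs with onset on or after the time of initiation of study drug administration". It adds: "All reported events will appear in AE listings, however only TEAE will be summarized".

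Protocol 8.5.4 collects AEs from the signing of consent and asks for start and stop dates. Footnote 1 to Tables 2.1 and 2.2 of the Protocol, with Protocol 7.1, places Baseline from 1 to 7 days after Screening.

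**The concern.** Setting a partial onset to the first-dose date is a reasonable convention when nothing else is known, because a doubtful event is then kept in the TEAE tables. It is not reasonable when the recorded stop date already shows that the event ended before dosing. The rule then overrides a known fact with an imputed one. The record carries an impossible date order, and an event that cannot be treatment-emergent is summarised as one.

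Long-term safety is a primary objective and the trial is small, so a single misclassified subject is visible in a preferred-term row. Because AE collection starts at consent, events that begin and end before dosing can be in the database.

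**Working it through.** The documents give no figure to reproduce. The check applies SAP 7.4 as written and classifies the result by SAP 8.6.1.

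**Worked examples** (assumed dates, first dose 20 March 2015)

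| Record | Known start | Known stop | Start imputed by SAP 7.4 | Result |
|---|---|---|---|---|
| AE, day missing | March 2015 | 17 March 2015 | 20 March 2015 | Start 3 days after stop; counted as TEAE |
| AE, month missing | 2015 | 17 March 2015 | 20 March 2015 | Same |
| AE, day missing, earlier month | February 2015 | 17 March 2015 | 1 February 2015 | Order correct; not a TEAE |
| Medication, month missing | 2015 | 25 February 2015 | 20 March 2015 | Start 23 days after stop |

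The third row marks the boundary: the rule misfires only when the known parts of the start match the first dose.

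**How often the rule misfires on records that are already eligible.** Take every first-dose date in a 365-day year, with each event starting *a* days and stopping *b* days before dosing, where 1 ≤ *b* ≤ *a* ≤ *W*. All combinations have equal weight. Each *a* allows *a* stop dates, so there are 365 × Σ*a* records.

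- Day missing, *W* ≤ 7: the onset falls in an earlier month for 12*a* of the 365 first-dose dates. The misfire share is Σ*a*(365 − 12*a*) / (365 Σ*a*).
  - *W* = 1: 353/365 = 96.7%.
  - *W* = 7: Σ*a* = 28 and Σ*a*² = 140, so (10,220 − 1,680)/10,220 = 83.6%.
- Month missing: the onset falls in an earlier year for *a* of the 365 dates. The share is Σ*a*(365 − *a*) / (365 Σ*a*).
  - *W* = 1: 364/365 = 99.7%.
  - *W* = 7: (10,220 − 140)/10,220 = 98.6%.
- Medications, *W* = 37 (30 days before Screening from SAP 8.6.3, plus up to 7 days to dosing): direct enumeration of 256,595 records gives 22.0% with the day missing and 93.2% with the month missing.

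These shares are conditional on a partial start and a known pre-dose stop. They are not expected event counts.

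**Effect on a table.** Protocol Amendment 2 gives 20 subjects, so one false TEAE moves a preferred-term incidence by 1/20 = 5 points, provided the subject has no genuine TEAE under the same term. With the 25 subjects still stated in SAP 3.5 it would be 1/25 = 4 points.

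**After the fix.** Where the stop precedes first dose, the start is set to the first day of the known month, or to 1 January if the month is missing. False TEAEs fall to 0 and records with start after stop fall to 0, in every window tested.

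**The case against.** The strongest reply is that this will hardly ever happen. It needs an AE that starts after consent, resolves before dosing within about a week, and has a complete stop date but an incomplete start. A missing month is implausible for an event only days old. AEs are asked about at every visit, SAP 7.1 sends incomplete data to Data Management before lock, and SAP 7.4 allows an imputed date to be replaced. Any residual error over-counts TEAEs and so would not hide a signal.

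The rarity and the direction stand. The safeguards do not close the gap. Data Management review offers only possible resolution. The replacement clause is optional, does not mention date order, and points towards the more conservative analysis, which for an AE normally means keeping it as treatment-emergent.

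A reader might also infer three wider consequences that the documents do not support:

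- *Apparent use of prohibited drugs.* The Protocol requires "a 21-day washout of any active pharmacologic vitamin D metabolite or its analog" (7.5.3.3), so washed-out drugs may well have a known pre-dose stop. But Protocol 7.6.2.8.6 defines a concomitant medication by its being taken after treatment starts. A drug stopped before dosing does not qualify, whatever start is imputed. Neither document says that classification uses the imputed start.
- *Wrong durations in the safety tables.* SAP 8.6.1 and 8.6.3 plan no AE or medication duration summary.
- *Harm from uncapped stop dates.* SAP 7.4 says "If the month is unknown, then assign 'December" for a stop date and sets no cap at last contact, data cut-off or death. This could put an odd date in a listing, but it is not shown to change any planned table.

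**Conclusion.** The point holds for AE start dates. Applied as written, SAP 7.4 and SAP 8.6.1 together can summarise as treatment-emergent an AE whose own stop date shows that it ended before the first dose. This is a stated rule that gives a wrong answer, not merely a missing detail.

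Its practical weight is low: a tidy-up that is worth making, not a threat to the safety conclusions. The rarity judgement rests on the 1-to-7-day gap. The incidence figure rests on 20 treated subjects. The misfire shares rest on uniform dates and equal weighting. No document gives the number of partial dates, so no expected count of affected events can be stated. For medications, the conclusion goes no further than a start after the stop in the data or listings.

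**What to change.** Add to SAP 7.4, for example: *A partial start date is imputed to the first-dose date only if the stop date is missing or falls on or after the first dose. If the stop date is known to precede the first dose, the start is imputed to the earliest date consistent with its known parts. An imputed start date may never be later than a known stop date.*

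For this purpose, a partial stop date should count as preceding the first dose only when its known parts establish that. For these records, the exact early date chosen does not alter their classification as not treatment-emergent.

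The cost is the SAP text above and a line of code. It needs no new data and no clinical decision, and it replaces case-by-case correction with a prespecified rule.

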## 7.5 Unscheduled or Early Termination Visits

In general, data collected by study visit will be summarized using the visit number specified in the database. Outcomes scheduled at a planned study visit but are collected during an unscheduled visit or early termination visit will be mapped into the closest study visit based on the study day of the unscheduled visit or early termination visit, and the schedule of assessment in the protocol.

For outcomes where both the planned study visit and an unscheduled visit or early termination visit corresponding to that study visit are both available, the planned study visit measurement will be used for the analysis.

All safety data including the planned study visits and unscheduled/early termination visits will be included in the shift tables.

All data will be included in the data listings and outcomes measured during unscheduled visits and early termination visits will be marked as acquired during an unscheduled visit.

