### 4.2 Pharmacodynamics Endpoints

The primary pharmacodynamics endpoints are:

- Number and percentage of subjects who have serum phosphorus levels which, at any time after dosing are in the normal range ( $\geq 2.5$  and  $\leq 4.5$ ) or outside the normal range
- Change from baseline in serum biochemistry parameters associated with XLH, as measured by serum phosphorus, iPTH, FGF23 (total and free), and  $1,25(\text{OH})_2\text{D}$
- Change from baseline in urinalysis parameters associated with XLH, as measured by 2-hour urine TmP/GFR and TRP, i.e., calcium, creatinine, and phosphorus
- Change from baseline in urine parameters associated with XLH, as measured by 24-hour urine, i.e., urinary phosphate, calcium, creatinine, and urine calcium/creatinine ratio
- Change from baseline in bone biomarkers associated with XLH, as measured by total ALP and BALP, CTx, and P1NP
- Change from baseline in fractional excretion of phosphorus (FEP), defined as  $100\% * (2\text{-hour urine phosphorus} * \text{serum creatinine}) / (2\text{-hour urine creatinine} * \text{serum phosphorus})$

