#### **8.7.1 Renal Ultrasound**

Renal ultrasound will be conducted with findings of nephrocalcinosis graded on a 5-point scale and by a central reader. These results will be summarized by time point. Furthermore, a grade shift table summarizing changes from baseline by time point will also be created.

The number and percentage of subjects with nephrolithiasis observed in the kidney will be summarized by time point. A shift table summarizing changes from baseline by time point will be created.

A listing of renal ultrasound nephrocalcinosis scores, the presence or absence of nephrolithiasis in the kidney and the radiologist's comments will also be provided.

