#### **8.7.2 ECG**

Descriptive statistics for the absolute measurements and changes from Baseline for selected ECG parameters will be reported. These include the following intervals: QT, QT corrected for heart rate, the time elapsed from the onset of atrial depolarization to the onset of ventricular depolarization (PR), and time elapsed for depolarization of the ventricles (QRS).

The frequency of subjects with a maximum increase from Baseline in the QTc interval will be summarized according to the following categories: >30 ms and >60 ms. In addition, the frequency of subjects with QTc post dose values according to the following categories: >450 ms, >480 ms and >500 ms, will be summarized.

A listing of all ECG parameters including the overall assessment will also be created.

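### Read literally, SAP 7.5 lets a planned value displace unscheduled and early-termination results in the QTc maximum and any-time phosphorus counts, and the renal ultrasound shift tables lack a one-record-per-subject rule

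*SAP*

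**What the plan says.** SAP 7.5 sets three rules for results obtained outside the planned visits.

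- **Mapping.** An unscheduled or early-termination result "will be mapped into the closest study visit based on the study day of the unscheduled visit or early termination visit", together with the protocol's assessment schedule. No maximum window is given.
- **Selection.** When the visit also has a planned result, "the planned study visit measurement will be used for the analysis". The sentence is not limited to any type of output.
- **Exceptions.** "All safety data including the planned study visits and unscheduled/early termination visits will be included in the shift tables". Also, "All data will be included in the data listings", with unscheduled and early-termination results flagged.

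The outputs affected are defined elsewhere in the SAP:

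- **QTc (8.7.2).** "The frequency of subjects with a maximum increase from Baseline in the QTc interval will be summarized according to the following categories": above 30 ms and above 60 ms. Post-dose QTc is also counted above 450, 480 and 500 ms.
- **Phosphorus (4.2).** The count is of subjects whose levels "at any time after dosing are in the normal range" or outside it. Section 8.8.1 adds an overall count of subjects who ever reached the range.
- **Renal ultrasound (8.7.1).** For nephrocalcinosis, "a grade shift table summarizing changes from baseline by time point will also be created". The nephrolithiasis shift table is also by time point.

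**The concern.** A maximum, an any-time count or a threshold count should draw on every post-dose value recorded. The QTc and phosphorus counts are frequency tables. They are neither shift tables nor listings, so neither exception in SAP 7.5 covers them, and neither section says that unscheduled values count.

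Some of the results at risk are likely to be informative. Protocol 7.5.3.6 has clinically significant abnormal laboratory results repeated and allows extra blood samples after certain adverse events. The phosphorus criterion for dose-limiting toxicity (protocol 7.5.3.13) needs a confirmed value. Footnote 21 of the protocol's schedule asks subjects who stop before Week 72 to return for the Week 72 assessments, which include an ECG. Long-term safety is a primary objective, so a QTc count that misses the last ECG of a subject who left early would be a real gap.

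In the renal ultrasound shift tables the difficulty is the reverse. All values enter, but nothing says which one represents a subject who has two scans at one time point.

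**Working it through.** The plan states no figure on this point, so there is none to reproduce. The check traces the rule on the SAP's own schedules. The QTc and phosphorus values below are invented for illustration.

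**Inputs**
- Planned ECGs: Weeks 0, 24, 48 and 72/ET (SAP Appendix 1).
- Planned phosphorus: Weeks 0, 2, 4, 6, 8, 10, 12, 24, 26, 28, 36, 38, 40, 48, 50, 52, 60 and 72/ET (SAP Appendix 1).
- N: 20 in the current protocol, about 25 in SAP 3.5.
- Assumption: the closest visit is the closest one at which that assessment is scheduled.

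**1. Reach of the mapping.** ECGs are 24 weeks apart, so any ECG between planned visits lies within 24/2 = 12 weeks of one. With complete planned data, every mapped ECG therefore meets a planned value.

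**2. Early-termination ECG at Week 56.** Distance to Week 48: 56 − 48 = 8. Distance to Week 72: 72 − 56 = 16. It maps to Week 48, and a planned Week 48 ECG displaces it. Appendix 1 labels the last time point 72/ET, which suggests Week 72 instead. The two places need reconciling.

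**3. Unscheduled ECG at Week 30.** Distances are 30 − 24 = 6 and 48 − 30 = 18, so it maps to Week 24. Let planned QTc be 420 ms at every visit and the Week 30 value 505 ms.
- Under the rule, the maximum is 420 ms and the increase is 0.
- With all values, the maximum is 505 ms and the increase is 505 − 420 = 85 ms.
- The subject is missed in all five categories: increases above 30 and 60 ms, and values above 450, 480 and 500 ms.

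**4. Unscheduled phosphorus at Week 65.** Distances are 65 − 60 = 5 and 72 − 65 = 7, so it maps to Week 60. With 3.2 mg/dL at every planned visit and 4.8 at Week 65, the subject is never outside the range under the rule but is outside it with all values.

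**5. Weight of one subject.** 1/20 = 5 points; 1/25 = 4 points. Exact (Clopper-Pearson) 95% intervals:

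| N | 0 subjects | 1 subject |
|---|---|---|
| 20 | 0 to 16.8% | 0.1 to 24.9% |
| 25 | 0 to 13.7% | 0.1 to 20.4% |

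**6. Renal ultrasound shift table.** If 20 subjects each have a Week 24 scan and one has a further scan mapped to Week 24, and all values are tabulated, there are 20 + 1 = 21 entries, and 21/20 = 105% of N.

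**The case against.** The strongest reply is that SAP 7.5 was meant only for by-visit summaries. It opens by speaking of data collected by visit, and it can be read as a rule for make-up visits and duplicates. The endpoint wording (any time, ever, maximum, post-dose) would then govern. The literal reading also gives an odd result: a post-dose ECG at Week 5 maps to Week 0 and yields to the pre-dose baseline. This reading is possible. But the SAP does not state it, and naming shift tables as an exception suggests that other analyses follow the rule. Even if it is right, the SAP has no explicit rule for these values in the maximum and any-time counts, and the same clarification is needed.

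The second reply is that abnormal results have other routes. Clinically significant laboratory and ECG changes are recorded as adverse events where appropriate (protocol 7.5.3.1), new ECG abnormalities as treatment-emergent events (protocol 7.5.3.10), and hyperphosphataemia is an event to monitor (SAP 5.7). This stands as mitigation, but it does not correct the counts. The protocol's count of subjects with abnormal laboratory results (7.6.2.8.2) is not a shift table either, so the same rule literally reaches it.

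Third, for the count of subjects who ever reached normal phosphorus, leaving values out is conservative: adding them can only keep or raise it. That is correct. A reader might infer that the rule flatters the drug throughout; the documents do not support that.

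**Conclusion.** The point holds on the literal text of SAP 7.5. Unscheduled and early-termination results are left out of the QTc maximum and threshold counts and the any-time phosphorus counts when the planned value at the mapped visit exists. The renal ultrasound shift tables leave open that one subject is counted twice at a time point.

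The size is unknown. One affected subject is 5 points at N=20 or 4 at N=25. No section expressly plans unscheduled ECGs, so the clearest ECG case is the early-termination visit that the protocol requests. The Week 56 example rests on the mapping assumption stated in the working and on a planned Week 48 ECG being present.

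Three stronger conclusions are tempting but not supported:

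- That these values are discarded. They stay in flagged listings, enter the safety shift tables, and are used when the planned value is missing.
- That double counting is prescribed, or extends to echocardiography. SAP 7.5 and 8.7.1 only fail to exclude it for renal ultrasound. In SAP 8.7.3 the by-visit display describes the descriptive statistics, and the echocardiogram shift tables are not said to be by time point.
- That harm is known to be understated. Some off-schedule results will be make-up or routine early-termination visits, and how often an abnormal one would be displaced cannot be told from the documents.

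**What to change.** Amend SAP 7.5 in three respects:

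1. Limit the planned-value rule to by-visit summaries and GEE models.
2. State that maximum, threshold, ever and any-time summaries (the QTc categories, and phosphorus in or outside range) use all post-dose values: planned, unscheduled and early termination.
3. For the renal ultrasound shift tables, take one record per subject per time point, for example the worst.

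In the same edit, reconcile the nearest-visit mapping of early-termination results with the 72/ET label in Appendix 1.

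The cost is a few sentences and minor programming. Safety counts may look slightly less favourable. The ever-normal phosphorus count can only stay the same or rise, so report the by-visit proportions beside it.
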